SAGES II: Surgical patients will be identified from the operating room advanced booking schedule of Beth Israel Deaconess Medical Center (BIDMC), Brigham and Women's Hospital (BWH) and BWH-Faulkner according to procedures used successfully in SAGES I and recent pilot studies. Initial screening will be conducted using data from the electronic medical record.

The patient's surgeons will give the potential subjects general information about the research and we will send recruitment letter signed by the surgeon and study PI to potential participants. We will include an OPT OUT possibility. The address of each letter will be double checked before sending to ensure that the letter is properly addressed.

If no telephone call to opt out of the study is received, a study staff member will call the potential participant for a brief telephone screening assessment, with scheduling of a face-to-face visit in their choice of either their home or at the hospital (clinic visit or CRC), according to the patient's preference.

B.6.3. Consent and Capacity Assessment

For both SAGES I and II, patients will be asked to provide informed consent for participation in this study using a written form approved by the BIDMC and BWH and BWH Faulkner Institutional Review Boards. Informed consent will be obtained by trained study personnel following standard protocols. The consent will include a Health Insurance Portability and Accountability Act (HIPAA)-compliant consent form to obtain medical records from outside hospitals. This request for outside medical records is a procedure that has been approved previously for the first cycle of the PPG. For remote visits, a copy of the consent form will also be dropped-off in a contactless manner and a member of the research team will consent participants remotely (by phone or videoconference using an IRB approved platform like zoom or Starleaf). The signed consent form will be picked up in a contactless manner and signed by a member of the research team prior to starting the baseline interview. If possible we may conduct the consent procedures electronically, using the hospital- approved secure REDCAP (Research Electronic Data Capture). Participants may also choose to sign the consent form and mail it back with a stamped and pre-addressed envelope or scan/fax it back with wet signature before the interview. The study investigators and project coordinators will be available to the participants to answer any questions.

The SAGES I full cohort consent form is reviewed under protocol number 2009P-000262.

For the SAGES I SELECT cohort, six separate consent forms will be used. One consent form for the LP, one for the PET, one for phlebotomy procedures, one for the MRI procedures, one for TMS/EEG procedures and one for the amyloid PET.

For SAGES II, the overall consent form will include a request for permission for face-to-face and phone interviews, phlebotomy, daily hospital interviews, chart abstraction of the index hospitalization and re-hospitalizations, proxy interviews, as well as CSF collection at anesthesia induction before surgery. Three separate consent forms will be used in addition. Each one for the TMS/EEG PET, and one for the MRI procedures.

Participants who do not agree to the TMS portion of the study will be asked if they are willing to undergo an EEG recording alone. Participants will be verbally consented by study staff over the phone or inperson prior to the EEG.

For the standard consent procedures for the duration when home visits are not allowed, we will dropoff/pick-up the procedure consent (LP, PET, phlebotomy, MRI, and TMS/EEG) in a contact-free manner or mail or email the consent form with a stamped and pre-addressed envelope. A member of the research team will then consent participants by phone. Participants may sign the consent form and mail it back, or scan/fax it back with wet signature, or provide a wet signature in person at the procedure visits. If possible we may conduct the consent procedures electronically, using the hospital- approved secure REDCAP (Research Electronic Data Capture).

Capacity Assessment: All patients will be assessed for their ability to provide consent with a capacity questionnaire that is already being used for the SAGES I cohort. The capacity assessment takes place immediately after the consent document has been reviewed with the subject and before we ask the subject to sign the consent form.

The research assistant (RA) will tell the potential participant that they would like to verify their understanding of what the study is about and about their rights as a study participant. The RA then asks in total 5 questions about the ability to evidence choice, to understand relevant information and risk factors, and to appreciate the situation and its likely consequences. Answers are coded as either correct or incorrect. If two or more answers are incorrect, the potential participant is not eligible. If the RA thinks a potential participant does not have capacity or is unsure how to code the answers, they will write down the answers of the potential participant verbatim. For SAGES I SELECT, as described above, if a participant *is not able to give consent, we will ask the participant for assent and ask a proxy to provide the written consent.* For SAGES II, all subjects with unclear capacity will be adjudicated immediately via a conference phone call with the study director and a physician investigator on call. Eligibility decisions will be conservative to ensure that all enrolled participants have full capacity to consent.

After capacity to consent has been verified, we will ask the subject to sign the consent form.

Capacity to give consent will be re-assessed during the follow-up period, if the

- a. participant cannot remember ever enrolling in the study or if the
- b. participant cannot remember previous study visits or if the
- c. the participant is not aware that study participation is voluntary.

If there is any concern, we will conduct a verbal follow-up consent and re-assess participant's capacity with our capacity form. If the participant has impaired capacity to give consent, a legally authorized representative (spouse, adult child, parent, sibling, and other relative or close friend) or a legal guardian will be asked for consent. In this case, the patient will still be asked for assent to participate.

B.6.4.Subject Protection

Our study may involve the vulnerable population of cognitively impaired older persons. At baseline, due to our strict eligibility criteria excluding dementia patients, we anticipate that all of our study patients will be cognitively intact and able to give informed consent. At the time of each subsequent study assessment, we will seek assent from each patient for continued participation in the study. The patient may refuse continued participation at any time. If significant cognitive impairment develops during the course of this study, then assent for continued participation will also be sought from a family member or legal guardian. This dual procedure has been previously approved and successfully applied in our previous studies involving similar study populations.

B7. STUDY LOCATION

Privacy

The comfort and privacy of patients will be protected during every phase of the study by carefully trained research staff. The informed consent, eligibility assessments and clinical procedure will occur in a private room at the BIDMC CRC (LP and TMS-EEG), in the MRI research area (MRI), in patients' homes (baseline and follow-up assessments), or remotely via telephone or videoconference.

All subjects will have the chance to have their questions answered by one of the study's staff or investigators during this visit.

Physical Setting

Baseline and follow-up assessments will occur in the patient's choice of their homes (in-person or remotely via telephone or videoconference using an IRB approved platform like zoom or Starleaf), at Hebrew Senior life, or at a clinic visit. Space will be provided for interviewing in the BIDMC Clinical Research Center (CRC) if needed. A "SAGES Screening and Safety Procedures During COVID19" information sheet will be provided to participants prior to the baseline visit. Baseline and 1 month follow-up phlebotomy will occur in patient's homes (in-person or remotely via telephone or videoconference) or at the CRC. The research team will follow current BIDMC and Hebrew SeniorLife guidance to determine if a visit should be conducted in-person or remotely. As part of a remote visit, sanitized equipment and materials (iPad, iPad stand and set-up instructions, face mask and sanitizer bottle or wipes) for the visit may be dropped off/picked up in a contactless manner by a member of the study team. For remote visits, a copy of the consent form will also be dropped-off in a contactless manner and a member of the research team will consent participants remotely (by phone or videoconference). The signed consent form will be picked up in a contactless manner and signed by a member of the research team prior to the baseline interview starting. The contactless drop-off, study visit, and pick-up may occur on separate days so as not to be too overwhelming for participants during a single visit.

We will retain all options for mode of administration due to the uncertainties with the COVID-19 situation--with clearance for remote or telephone during the time of COVID-19, and for any mode once we are allowed back in the homes. We will also discuss possible visit modes with the participants and follow their preference for the mode of the visits.

BIDMC:

- Patient enrollment, daily interviews and POD1 and 2 phlebotomy will occur on the surgical units of BIDMC and BWH. Daily interviews may be conducted in-person or remotely via telephone or videoconference. The research team will follow current hospital guidance to determine if a visit should be conducted in-person or remotely.
- LPs,TMS-EEG, and phlebotomy will be obtained at the CRC
- Specimen will be processed at the CRC or at the Boston Children's Hospital IDDRC Molecular Genetics Core Facility,

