A.3.2.5. PET: PET scans will take place under supervision of the NMMI faculty and staff. At the beginning of the session, an intravenous catheter will be placed in the antecubital vein of the left arm to participants prepositioned in the bed of the PET scanner or in an adjacent room prior to the scan. This will be used to inject the F¹⁸ Florbetapir radiotracer as a slow intravenous bolus (up to 15 mCi will be administered). The catheter will be removed after the injection. The catheter will be placed by and accessed by a certified nuclear medicine technician. F¹⁸ Florbetapir PET will be acquired with an 370 MBq (10.0 mCi) \pm 10% bolus injection followed by 20 min (4X5min frames) acquisition at 50-70 min post-injection as in the acquisition protocols used in ADNI (ADNI 3). Participants are scanned on a Siemens Biograph m64 time-of-flight PET/CT. Subjects will be instructed to remain still, with eyes open or closed depending on the scan sequence, for the total duration of the scan. The duration of the visit itself will be approximately 2-3 hours (consent, preparation, injection, and 20 min of scanning starting at 50 min after injection.

If a participant wants results of their PET scan released to their physician, they may request it. [name] will communicate with the BIDMC Department of Nuclear Medicine who will access the database and release an unblinded report to [name] and to the OMR. [name] will relay the report and information to the patient's physician, and alert them also that the report and scan can be obtained through the BIDMC Medical Records department. Thus, the report and scan should be accessible through regular channels by all physicians both within and outside the BIDMC system.

A.3.2.6. TMS-EEG: These procedures will take about 4-5 hours. All SAGES I SELECT participants will undergo the first TMS-EEG visit with theta burst stimulation targeted at one of the brain regions identified above (section A.2.5 Project 5) and following procedures as described above. We will then invite all participants back for a second and third time to target the theta burst at the other 2 brain regions within a 6-week timespan after the initial TMS-EEG session.

TMS-EEG Procedures (SAGES I SELECT and SAGES II cohorts):

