7. Risk of PET: The primary risk related to PET is that of radiation exposure associated with the injected radiotracers and accompanying CT. The effective dose resulting from a 370 MBq (10 mCi) dose of Amyvid is 7.0 mSv in an adult (19 x 370 = 7030 μ Sv = 7.030 mSv). The use of a CT scan to calculate attenuation correction for reconstruction of Amyvid images (as done in PET/CT

imaging) will add radiation exposure. Diagnostic head CT scans using helical scanners administer an average of 2.2 ± 1.3 mSv effective dose (CRCPD Publication E-07-2, 2007). Given that the actual radiation dose is operator and scanner dependent, the total radiation exposure from Amyvid administration and subsequent scan on a PET/CT scanner is estimated to be 9 mSv over a single year of the study. The organ that receives the maximum exposure is the gallbladder. The overall effective and maximum organ-specific doses are well below the 21 CFR 361.1 guidelines for RDRC approved studies. The radiation doses for each PET scan are not themselves expected to produce any harmful effects, although there is no known minimum level of radiation exposure considered to be totally free of the risk of causing genetic defects or cancer. The risk associated with the amount of radiation exposure participants receive in this study is considered low and comparable to everyday risks. Given our minimum enrollment age of 70 years old for SAGES I participants, the issue of risk of pregnancy and inadvertent radiation exposure to a fetus will not be an issue for this study, and no pregnancy tests will be required.

There is a minimal risk associated with a potential idiosyncratic or allergic reaction to the tracer or any element contained in the injection. While these are so rare their frequency is not well-reported, but we have protocols in place to address any potential adverse reactions to the procedure or tracer. There is a minor risk associated with the venipuncture, placement of an intravenous catheter, and radioisotope injection. These risks include pain, bruising, or painful infiltration of a failed injection. Given our highly trained staff, we anticipate that these complications will occur in less than 1:20 cases.

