7. Protection against risk related to PET: For SAGES I SELECT and SAGES II, all PET scans will be performed by experienced, certified nuclear medicine technologists, who have been well-trained to perform PET imaging studies. To minimize risks of radiation exposure, the lowest possible dose of radioactivity compatible with good image quality will be used. The radiation exposure for amyloid (annual effective dose exposure of 7 mSv (without CT) and 9mSV (with CT) over a single year of the study) is very low and well within FDA guidelines for research. These doses are similar to those used in standard medical tests, and have risks that are so low they are difficult to estimate, and are considered to be comparable to everyday risks of exposure. We will also assure that participants have not exceeded recommended radiation exposure risks overall). To be eligible for any PET scan, participants must not have received any prior scan with radioactive agents either for clinical or research purposes within 12 months, such that the total research-related radiation dose to the participant in any given year should not exceed the limits set forth in the US Code of Federal Regulations (CFR) 21, Section 361.1. There is also risk of Idiosyncratic or allergic reaction to injection of tracer. The amount of tracer injected is so small that participants should not experience any side effects. However, if any of these should occur, participants are instructed to inform research staff immediately. We will have clinicians on-call to address any reported adverse reactions following the procedures, and already have standard protocols in place to address any untoward reactions.

The updated consent form for the PET scan informs the participants about the benefits and risks of disclosure of results. We will send a letter to participants who already consented to the PET scan also outlining the benefits and risks. If these participants want to share the PET scan results with their

doctor, they would need to review and sign the updated consent form.

B.5.3. Analysis of Risk/Benefit Ratio

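### Section A.3.2.5 states two different maximum florbetapir activities (15 mCi and 11 mCi), and the protocol's radiation exposure is worked out at 10 mCi only

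*Protocol*

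**What the plan says.** The injected activity appears twice in Protocol A.3.2.5 (PET). The sentence on the catheter says the tracer is given "as a slow intravenous bolus (up to 15 mCi will be administered". After two sentences about the catheter, the acquisition sentence says that florbetapir PET "will be acquired with an 370 MBq (10.0 mCi", with a tolerance of plus or minus 10%. A.4.8.1 offers PET to SAGES II participants without CSF under the same procedure, so both statements apply in both cohorts.

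The exposure estimate is in B.5.1 item 7: "The effective dose resulting from a 370 MBq (10 mCi) dose of Amyvid is 7.0 mSv in an adult", obtained as 19 times 370. It adds a head CT with an "average of 2.2 ± 1.3 mSv effective dose", and the total "is estimated to be 9 mSv over a single year of the study". B.5.2 item 7 repeats the result: "annual effective dose exposure of 7 mSv (without CT) and 9mSV (with CT". Neither section gives an exposure for any activity above 10 mCi.

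Three other statements rely on these figures or bear on them. B.5.1 concludes that whole-body and organ doses lie well below the 21 CFR 361.1 guideline. B.5.2 commits to the lowest activity that still gives good images. The PET exclusion criterion in C.1.1, repeated in B.5.2, turns on whether the total research-related radiation would exceed the 21 CFR 361.1 limits.

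**The concern.** A stated maximum defines what staff are authorised to inject. Here the section gives two. An injection of 12, 13 or 15 mCi complies with the first sentence and is a deviation under the second, and neither the site nor a monitor can tell from the text which applies.

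The risk assessment is tied to one of the two statements. If the higher ceiling stands, the 7 and 9 mSv in the risk sections describe less exposure than the protocol permits. The 21 CFR 361.1 comparison has then not been shown at the permitted maximum. An eligibility check on cumulative research dose that uses 9 mSv for this scan could also understate a participant's total.

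**Working it through.** **Inputs, all from the Protocol**

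- Ceiling: 15 mCi (A.3.2.5).
- Acquisition activity: 370 MBq = 10.0 mCi, plus or minus 10% (A.3.2.5). This also fixes the conversion, 37 MBq per mCi.
- Dose coefficient: 19 µSv per MBq (B.5.1 item 7).
- CT: 2.2 ± 1.3 mSv (B.5.1 item 7).

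**Formula.** Tracer dose in mSv = 19 × activity in MBq / 1000. Total = tracer dose + 2.2.

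**Step 1: reproduce the stated figures (10 mCi).** 19 × 370 = 7030 µSv = 7.03 mSv, stated as 7.0. With CT, 7.03 + 2.2 = 9.23 mSv, stated as 9. Both reproduce.

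**Step 2: top of the tolerance (11 mCi).** 11 × 37 = 407 MBq. 19 × 407 = 7733 µSv = 7.7 mSv. With CT, 7.73 + 2.2 = 9.9 mSv.

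**Step 3: the ceiling (15 mCi).** 15 × 37 = 555 MBq. 19 × 555 = 10,545 µSv = 10.5 mSv. With CT, 10.545 + 2.2 = 12.7 mSv.

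| Activity | MBq | Tracer, mSv | With mean CT, mSv | With CT 2.2 ± 1.3, mSv |
|---|---|---|---|---|
| 10 mCi (basis of the stated figures) | 370 | 7.0 | 9.2 | 7.9 to 10.5 |
| 11 mCi (upper tolerance) | 407 | 7.7 | 9.9 | 8.6 to 11.2 |
| 15 mCi (ceiling) | 555 | 10.5 | 12.7 | 11.4 to 14.0 |

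**Step 4: size of the gap.**

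- Activity: 15/10 = 1.5 times the nominal value, and 15/11 = 1.36 times the upper tolerance.
- Tracer dose: 10.545/7.03 = 1.50, so 50% above the stated 7.0 mSv.
- Total: 12.745/9 = 1.42 against the rounded stated figure, or 12.745/9.23 = 1.38 against the unrounded one. Either way this is about 40%.

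**The case against.** The best defence is that the two sentences do different jobs. One sets a ceiling; the other gives a nominal activity with a tolerance. Any injection of 9 to 11 mCi satisfies both, so staff can comply with the whole section, and the acquisition sentence says how scans are to be done. B.5.2 also promises the lowest workable activity, and the PET exclusion criterion guards against exceeding the regulatory limits. On this view 12.7 mSv is a worst case that nobody intends.

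Much of this stands. The two statements are not mutually exclusive: the conflict is confined to activities above 11 and up to 15 mCi, and 12.7 mSv is the exposure at the ceiling, not an expected value. But neither the commitment to a low activity nor the exclusion criterion withdraws either statement. If the ceiling has no practical role, the text still authorises it without an exposure figure.

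A reader might infer three further things that the documents do not support:

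- **That participants are given an understated radiation figure.** B.5.1 and B.5.2 are protocol sections. The consent pages are not available for review, so what participants are told is unknown.
- **That a regulatory limit is breached.** The protocol cites 21 CFR 361.1 but gives no numerical limit, so nothing here shows that 12.7 mSv would change its conclusion. The comparison has simply not been shown at the permitted maximum.
- **That varying activity would degrade the amyloid classification used in Projects 1 and 3.** The protocol gives no positivity threshold, noise figure or variance linking activity to misclassification. PET is also only the fallback where CSF is not obtained, and the number of scans is not stated.

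**Conclusion.** The point holds as an internal inconsistency with a safety consequence. A.3.2.5 gives two maximum activities, 15 mCi and 11 mCi, and nothing elsewhere in the protocol settles which governs. The exposure stated in B.5.1 and B.5.2 is arithmetically correct at 10 mCi but does not cover the higher maximum, where the protocol's own inputs give 10.5 mSv from the tracer and 12.7 mSv with mean CT.

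These figures assume that dose scales in proportion to activity, as the protocol's own calculation does, and that the CT contribution does not depend on injected activity. They also read the tracer in A.3.2.5 and the product named in B.5.1 as the same agent. The protocol notes that actual dose depends on operator and scanner; over its stated CT spread the total at the ceiling runs from 11.4 to 14.0 mSv.

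No view is taken on which activity is right. Sample size, power, type I error and the analysis models are unaffected.

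**What to change.** 1. Reconcile the two activity statements in A.3.2.5 so that the section states one consistent permitted maximum. Which one is for the investigators and the responsible nuclear medicine and radiation safety staff to decide. A.4.8.1 then carries it into SAGES II without further change.
2. Restate the exposure figures in B.5.1 item 7 and B.5.2 item 7, with and without CT, for the maximum that the reconciled text permits, including any tolerance.
3. Repeat the 21 CFR 361.1 comparison at that maximum, and use the same figure when checking cumulative research dose for PET eligibility.
4. Check the PET consent form against the reconciled text, and amend it only if it differs.

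The cost is a wording amendment with IRB review, plus a consent revision if step 4 shows one is needed. No design, sample size or analysis change follows.
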